1.1 Trial Design

This study is a randomized, crossover, non-placebo controlled trial of 50 patients with history of breast cancer and bothersome hot flashes. We propose to have 25 patients per arm in a two-arm study randomized to Embr Wave device vs no device or other treatment for bothersome hot flashes with a 1-month crossover. *The study has enrolled 23 participants with no active subjects in follow up as of 01/05/2022. The current amendment version dated 1/5/2022 includes the following changes a) update the study intervention to recently launched Embr Wave Generation 2 device and b) enroll an additional 10 participants so that approximately 50% of the study population will use the Generation 2 device. This increases initial planned sample size of n=40 by an additional 10 subjects to n=50. Study design shown below in Figure 1.*

[Type here]

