4.2. Study Location and Sample

This study will be open for accrual at the Stefanie Spielman Comprehensive Breast Center and James Cancer Hospital. This trial will be conducted under the auspices of The Ohio State University. Testing will take place in clinics of the Stefanie Spielman Comprehensive Breast Center or done so virtually via phone and/or video calls. Patient eligibility will be determined according to the eligibility criteria listed. The study will enroll up to approximately 50 patients.

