10.0 CRITERIA FOR RESPONSE ASSESSMENT

All patients will be considered evaluable. Participants with only baseline measures will be considered as drop-outs.

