All analyses will proceed on an intent-to-treat basis. When observations of preliminary efficacy endpoints are missing, the rest of that patient's observations may still be used in the mixed effects model. To assess the potential impact of informative loss to follow-up, we will compare patients who leave the study or cease reporting endpoints to those who provide data for the full study duration. Patients will be compared on the basis of baseline variables and available longitudinal measurements. The pattern of loss to follow-up will be reported via CONSORT chart. Potential impact on estimates will be assessed via multiple imputation. For the purpose of evaluating compliance, patients who leave the study will be recorded as not wearing the device after leaving the study, ensuring that all patients are evaluable.

As an exploratory analysis, individual components of the HFRDIS will be analyzed using the same model as the total HFRDIS. As sensitivity analyses, the preliminary efficacy analyses will be repeated allowing for temporal correlation of measures, and including as covariates any baseline variables with large imbalances.

Our feasibility target is that at least 75% of all patients meet the compliance criteria described above. The minimum number of the 38 enrolled patients meeting the compliance criteria to achieve this threshold is 23 (77%), in which case the 95% Jeffreys interval lower bound is 60% (thus we can rule out population compliance rates below 60%) (Figure 3, left). We expect the population compliance rate to be at least 85%, in which case we have at least 93% probability of

[Type here]

achieving the compliance target (Figure 3, right). With a population compliance rate of 80%, we have a 76% probability of achieving the compliance target.

[figure not shown]

Figure 3: **Left:** Jeffreys intervals (95% equal tail probability credible intervals from a Beta(0.5, 0.5) prior) corresponding to various sample proportions with 30 patients. **Right:** Probability of achieving target compliance rate for various population rates.

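### The pass count for the primary feasibility target (23 of 38, labelled 77%) is wrong: 23/38 is 60.5%, the figures belong to n = 30, and the plan is for 50 patients

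*Combined protocol and SAP*

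**What the plan says.** The primary objective (Section 2.0) is feasibility, and Section 12.1 evaluates it first by device usage. Its success criterion is: "Our feasibility target is that at least 75% of all patients meet the compliance criteria described above". The next sentence turns this into a number of patients: "The minimum number of the 38 enrolled patients meeting the compliance criteria to achieve this threshold is 23 (77", with the bracket closing as 77%. It attaches a 95% Jeffreys lower bound of 60%, said to rule out lower population rates. The section then gives at least a 93% chance of meeting the target if the true rate is 85%, and continues: "With a population compliance rate of 80%, we have a 76% probability of" meeting it.

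Three sample sizes are in play. The sentence uses 38. The Figure 3 caption describes its left panel as "corresponding to various sample proportions with 30 patients". The trial itself is planned at 50: Section 1.0 lists 50 subjects, Section 1.1 says "This increases initial planned sample size of n=40 by an additional 10 subjects to n=50", and Section 4.2 says "The study will enroll up to approximately 50 patients".

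Attrition does not reduce the denominator. Section 10.0 says "All patients will be considered evaluable", and Section 12.1 counts those who leave as not wearing the device from then on, "ensuring that all patients are evaluable".

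**The concern.** The sentence contradicts itself, because 23 out of 38 is neither 77% nor at least 75%. It is also the only place where the target for the primary objective becomes a patient count. A reader is left with two pass rules, 75% and 23 patients, which agree only at n = 30, a size that appears nowhere else except in the Figure 3 caption. With 50 enrolled, any result from 23 to 37 compliant patients would pass on the count and fail on the percentage. A success criterion should not leave that choice open until the data are seen.

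**Working it through.** **Inputs (all from the plan).** Target 75% of all patients; count 23, labelled 77%; denominator 38 in the sentence and 30 in the Figure 3 caption; lower bound 60%; pass probabilities 93% at a true rate of 85% and 76% at 80% (Section 12.1). Planned size 50, previously 40 (Section 1.1).

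**Formulas.**
- Minimum count: k = ceil(0.75 × n).
- Jeffreys 95% lower bound: the 2.5% quantile of Beta(k + 0.5, n − k + 0.5), the prior named in the Figure 3 caption.
- Probability of meeting the target at true rate p: the sum over x = k to n of C(n, x) p^x (1 − p)^(n − x).

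**Step 1: reproduce the plan's figures.** With n = 30, k = ceil(22.5) = 23 and 23/30 = 76.7%. The 2.5% quantile of Beta(23.5, 7.5) is 59.6%. The pass probability is 93.0% at p = 0.85 and 76.1% at p = 0.80. These round to all four stated figures. A search over every count for n = 20 to 60 finds no other pair that does so, and 30 is the only n in that range whose minimum count is 23.

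**Step 2: test the sentence as written.** 23/38 = 60.5%, with a Jeffreys interval of 44.7% to 74.8%, wholly below the target. For n = 38 the minimum is ceil(28.5) = 29, so 23 is 6 short. For n = 50, 23/50 = 46% (interval 32.7% to 59.7%); the minimum is ceil(37.5) = 38, so 23 is 15 short.

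**Step 3: figures that follow from the 75% rule.**

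| n | Minimum count | Lower bound | P(pass) at 85% | P(pass) at 80% |
|---|---|---|---|---|
| 30 | 23 (76.7%) | 59.6% | 93.0% | 76.1% |
| 38 | 29 (76.3%) | 61.2% | 95.1% | 78.4% |
| 40 | 30 (75.0%) | 60.2% | 97.0% | 83.9% |
| 50 | 38 (76.0%) | 62.9% | 97.0% | 81.4% |

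**Step 4: allow for approximate enrolment.** Section 4.2 gives no lower limit, so 45 is my assumption.

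| n | Minimum count | Lower bound | P(pass) at 85% | P(pass) at 80% |
|---|---|---|---|---|
| 45 | 34 | 61.7% | 97.0% | 82.6% |
| 46 | 35 | 62.4% | 96.5% | 80.5% |
| 47 | 36 | 63.2% | 95.9% | 78.3% |
| 48 | 36 | 61.5% | 97.8% | 85.2% |
| 49 | 37 | 62.2% | 97.4% | 83.4% |
| 50 | 38 | 62.9% | 97.0% | 81.4% |

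**Step 5: effect of using 23 literally.** At a true compliance rate of 60%, the chance of reaching 23 is 54.4% with 38 patients and 98.4% with 50. The correct counts would pass such a device with probability 2.7% (29 of 38) or 1.3% (38 of 50).

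**The case against.** The governing criterion, 75% of all patients, stands directly before the faulty sentence, and the count carries a percentage that exposes the slip. This is a feasibility pilot, and no stopping rule or sample-size choice hangs on the count. At n = 50 the stated operating characteristics err on the cautious side: the claims of at least 93% and of excluding rates below 60% remain true, and 76% understates 81.4%. All of this stands. It means the intent can be recovered, and that the pass probabilities in Step 5 apply only if someone used 23 and ignored 75%; they should not be read as the expected behaviour of the trial.

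It is also possible that 38 was never meant as a denominator. It equals ceil(0.75 × 50), so it may be the updated count typed into the wrong place. The documents do not say so. If it is true, the 29-of-38 comparison is moot, but the sentence is still wrong and the n = 50 correction is unchanged.

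Finally, Figure 3 could not be seen. The caption ties only its left panel to 30 patients; that the right panel also uses 30 is inferred from the 93% and 76% in the text. None of these points makes the stated count correct.

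**Conclusion.** The concern holds. The pass count for the primary feasibility target is wrong for every denominator from 20 to 60 except 30, and the section's two sample sizes, 38 and 30, both differ from the planned 50. The material error is in the count and the denominator: 38 of 50 are needed, not 23. The attached probabilities and lower bound are out of date rather than misleading. The conclusion rests on the 75% target being the intended rule, on all enrolled patients being in the denominator as Sections 10.0 and 12.1 say, and on about 50 being enrolled. If between 45 and 50 enrol, the count is 34 to 38, the lower bound 61.5% to 63.2%, and the pass probability 95.9% to 97.8% at a true rate of 85% and 78.3% to 85.2% at 80%. It should be corrected before the compliance data are read.

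**What to change.** Replace the sentence and the probabilities after it with a rule that holds for any enrolment, followed by the planned case. For example:

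> Feasibility is shown if the number of compliant patients is at least ceil(0.75 × number enrolled). With 50 enrolled the threshold is 38 (76%), where the 95% Jeffreys lower bound is 63%. The chance of reaching it is 97% if the true compliance rate is 85%, and 81% if it is 80%.

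Check both panels of Figure 3, redraw for n = 50 any drawn at n = 30, and correct the caption. Remove 38 as a denominator, or explain it.

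This costs one paragraph and one figure, with no new data and no more patients. One related gap is a separate matter: Section 12.1 refers back to compliance criteria but gives only minutes and sessions per day, without a per-patient cut-off. No count can be applied until the study team sets one, so it is sensible to add that sentence in the same amendment.
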